3.4.5.2 Other Secondary Efficacy Analyses

Analyses for the proportions

The primary estimand of the proportions of subjects is defined as follows:

- Population: Subjects in the FAS.
- Variable (endpoint): responder at Week 26 or at Week 52, where a responder is defined as a subject who meets all the criteria listed in the corresponding endpoint. For example, a subject will be considered as a responder of 3-point improvement in MGADL score at Week 26 if this subject achieved (1) ≥ 3 -point improvement in MG-ADL score at Week 26 and (2) no use of rescue therapy between Day 28 and Week 26.
- Intercurrent event:

[REDACTED]

- Population-level summary: difference of the inebilizumab vs placebo groups in the proportion of the responders regardless of treatment discontinuation.

Subjects will be considered as non-responders if they discontinue from the study before the timepoint of interest (Week 26 or Week 52).

The estimate of the treatment effect estimator will be evaluated using [REDACTED] logistic regression [REDACTED]

[REDACTED]

Analyses for the changes from baseline

The primary estimand of the change from baseline is the same as the one defined for the key secondary endpoints as mentioned in Section 3.4.3.2. The estimate of the treatment effect estimator will also be based on a contrast from an MMRM approach [REDACTED]

[REDACTED]

Analyses for the time to first exacerbation

An exacerbation is defined as one of the following:

[REDACTED]

[figure not shown]
[REDACTED]

The time to first exacerbation will be analyzed utilizing treatment- policy strategy. The primary estimand of the time to first exacerbation is defined by the following:

- Target population: Subjects in the FAS
- Variable: Time in days from Day 1 to the date of the first exacerbation by the timepoint of interest (Week 26 or Week 52).
- Intercurrent event: All data captured from Day 1 to the timepoint of interest will be used for analysis. Subjects who do not complete the timepoint of interest and who don't have an exacerbation between Day 1 and the timepoint of interest will be censored at the time of discontinuation from the study or at the timepoint of interest, whichever is earlier.
- Population-level summary: Hazard ratio (HR) between inebilizumab versus placebo.

[figure not shown]
The hazard rate in the inebilizumab group will be compared to that in the placebo group using a Cox proportional hazard model [REDACTED]

[REDACTED]

[figure not shown]

3.4.6 Exploratory endpoints and Analyses

3.4.6.1 Exploratory Endpoints

3.4.6.2 Exploratory Endpoint Analyses

3.4.7 Subgroup Analyses

To explore the consistency of treatment effect, subgroup analyses will be performed on the FAS for the primary and the key secondary endpoints in the following subgroups as appropriate.

[REDACTED]

These analyses are to be considered as exploratory and will be performed on the FAS. Interaction tests would be conducted to evaluate the consistency of the treatment effect among the different categories of each subgroup variable.

[REDACTED]

3.5 Safety Analysis

The safety endpoints will be summarized for the RCP, OLP, combined RCP and OLP, and SFP, separately, and analyzed using treatment-policy strategy.

[REDACTED]

During the RCP, the safety analysis will be based on the safety analysis set. For the treatment-policy strategy, the analyses will include all data captured after Day 1 in RCP to the last scheduled visit in the RCP regardless of the rescue therapy use. [REDACTED]

For the combined RCP and OLP, the safety analysis will be based on the any inebilizumab analysis set using treatment-policy strategy. The analyses will include all data captured after the first IP or first inebilizumab administration date to the last scheduled visit in the OLP regardless of the rescue therapy use.

For the SFP, safety analysis will be summarized using treatment-policy strategy. The summary will include all data captured between Day 1 of SFP and the last scheduled visit in the SFP regardless of the rescue therapy use.

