### 2.1.4 Risk Assessment for Inebilizumab

Identified risks for subjects treated with inebilizumab are IRRs, [REDACTED], neutropenia, lymphopenia, and arthralgia.

In the NMOSD study, IRRs occurred at similar rates in the inebilizumab and placebo groups (9.2% and 10.7%, respectively). All IRRs in the study were Grade 1 or 2 (mild or moderate) in severity. To reduce the risk and frequency of IRRs, all subjects in the present study will receive prophylaxis with IV methylprednisolone, oral diphenhydramine, and oral acetaminophen, or equivalent. In the NMOSD study, laboratory abnormalities were observed in some subjects.

After 2 years of inebilizumab treatment, severe hypogammaglobulinemia (IgG < 200 mg/dL) was observed in 1/81 subjects (1.2%); this case of severe hypogammaglobulinemia occurred after plasma exchange (PLEX) and was transient. Neutrophil counts between  $1.0\text{--}1.5 \times 10^9/\text{L}$  were observed in 6.9% of inebilizumab-treated subjects vs 1.8% of placebo-treated subjects. Neutrophil counts between  $0.5\text{--}1.0 \times 10^9/\text{L}$  were observed in 1.7% of inebilizumab-treated subjects vs 0% of placebo-treated subjects. Neutropenia was generally transient and not associated with serious infections. Subjects in the present study will be monitored for neutropenia, and the IP will be discontinued if there is persistent Grade 3 neutropenia. A reduction in lymphocyte counts can be observed with inebilizumab, consistent with its mechanism of action.

In the NMOSD study, the proportion of subjects with arthralgia was numerically higher in the inebilizumab group than in the placebo group (9.8% vs 3.6%) during the RCP (Cree et al, 2019). The rate of arthralgia was lower in the combined RCP and OLP inebilizumab population (5.36 per 100 person-years) than in the RCP inebilizumab population (20.6 per 100 person-years).

Based on its mechanism of action and nonclinical and clinical data, other important potential risks of inebilizumab are serious infection, cytopenia, hypersensitivity (including anaphylaxis and serious skin reactions), immune complex disease, and PML. One case of possible PML was reported in the NMOSD study, though evaluation could not confirm PML in that case. No cases of immune complex disease were reported in any inebilizumab studies.

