## 7.2.2 Rescue Medications

Worsening of symptoms in MG can occur due to precipitating factors that include disease progression, infection, tapering of therapies, or certain medications ([Wendell and Levine, 2011](#)). This worsening can range from mild to severe. Rescue therapy can be used in any of the following circumstances:

1. QMG score is  $\geq 4$  points higher than the baseline score, or
2. QMG score increases  $\geq 4$  points between study visits, or
3. The Investigator is concerned that the subject's health is in jeopardy (eg, significant worsening of bulbar function).

The protocol-allowed rescue therapy options include IVIg or PLEX. Intravenous Ig is recommended over PLEX for subjects in this study since PLEX may remove the IP from circulation, thus potentially decreasing its therapeutic effect (Khatrī et al, 2009). Subjects who are treated with a protocol-allowed rescue therapy can continue in the study. High-dose corticosteroids are not a protocol-allowed form of rescue therapy (eg, IV methylprednisolone).

Rescue therapies should be recorded on the study's rescue therapy dedicated eCRF pages.

Rescue therapy is considered standard of care treatment; information about Sponsor coverage of out-of-pocket costs incurred by subjects treated with rescue therapy will be included in the site contract.

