#### 9.4.8 Pharmacokinetics Analysis

PK analyses will be based on the PK Analysis Set. Descriptive statistics of inebilizumab concentration data will be summarized.

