3.4 Analyses Methods

3.4.1 Intercurrent events and Strategies

Potential intercurrent events such as discontinuing from the treatment, early discontinuing from the study, death, or initiating rescue therapy, which includes intravenous immunoglobulin (IVIg) or plasma exchange (PLEX), may occur during the study. Subjects who discontinue from the treatment and/or receive rescue therapy will be encouraged to stay in the study after those intercurrent events and data will be collected through planned study completion. These intercurrent events will be addressed using different strategies in the efficacy and safety analyses as appropriate. The following analyses strategies will be used and detailed components of each strategy are included in the sub-sections under Section 3.4 and Section 3.5.

Treatment-policy strategy: The analyses will include all data captured in each study period, defined as the period after randomization to the conclusion of the last scheduled visit in the corresponding study period regardless of the rescue therapy use.

While on-treatment strategy: The analyses will include all data captured while subjects are on treatment during the RCP, [REDACTED]

All efficacy analyses described below apply to the RCP unless stated otherwise. The efficacy endpoints will be analyzed in the overall study population, AChR-Ab+ population, and MuSK-Ab + population, respectively, [REDACTED] as suitable. Supplementary analyses using treatment-policy strategy will be conducted for primary endpoint and key secondary endpoints to assess the robustness of the conclusions. For subjects in the OLP, the efficacy may also be summarized based on OLP and the combined RCP and OLP using treatment-policy strategy, if applicable.

The safety endpoints will be summarized for the RCP, OLP, **and combined RCP and OLP** separately and analyzed using treatment-policy strategy. Summary of AEs/ SAEs/ AESIs, CD20+ B-cell count, and Serum Immunoglobulins would be provided for subjects based on combined RCP and OLP, and based on SFP if applicable.. [REDACTED] may be conducted using while on-treatment strategy for TEAE/TESAE/AESI as needed.

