3.5.2 Clinical Laboratory Evaluation

[figure not shown]
The lab data will be summarized for RCP, OLP, combined RCP and OLP, and SFP, respectively. The analyses for the laboratory results are listed in Table 7. The toxicity will be

summarized using NCI-CTCAE version 5 for the tests with objective criteria and NCI-CTCAE version 4 was used for the tests with subjective criteria. The international system of units will be used for all the lab data.

Table 7 Laboratory Results Analysis

Laboratory dataset	Planned Analysis
Hematology and Chemistry	
 • Summary of worst post-baseline toxicity grade • Summary of at least 2-grade shift from the baseline to the worst post-baseline toxicity grade • Summary of shift from the baseline relative to the normal range • Summary of observed values, change from baseline and percent changes from baseline •
Immunoglobulins	
 • Summary of observed values and changes from the baseline

To evaluate the association between reduced Ig levels and infections/serious infections /opportunistic infections, **proportions of subjects with these AEs** will be summarized by the worst Ig Level during the combined RCP and OLP by the categories listed in [REDACTED]. **Additionally, TEAEs by SOC and PT during the combined RCP and OLP will be summarized by the categories listed in [REDACTED] as well.**

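### Immunoglobulin summaries and worst-Ig categories keep values taken after IVIg or PLEX rescue, with no visible rule to separate rescue effect from drug effect

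*SAP*

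**What the plan says.** SAP 3.5 applies treatment policy to the safety endpoints. For the RCP the analyses "include all data captured after Day 1 in RCP to the last scheduled visit in the RCP regardless of the rescue therapy use". For the combined RCP and OLP they run "to the last scheduled visit in the OLP regardless of the rescue therapy use". SAP 3.4.1 names serum immunoglobulins among the results to be summarised over the combined RCP and OLP.

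In SAP 3.5.2 (Table 7) the planned Ig analysis is "Summary of observed values and changes from the baseline". The same section tabulates infections, serious infections and opportunistic infections by each subject's worst Ig level over the combined RCP and OLP.

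On rescue, Protocol 7.2.2 says: "The protocol-allowed rescue therapy options include IVIg or PLEX". It recommends IVIg over PLEX because "PLEX may remove the IP from circulation, thus potentially decreasing its therapeutic effect". Protocol 2.1.4 reports one subject in 81 with IgG below 200 mg/dL after two years of inebilizumab in the NMOSD study, and adds that "this case of severe hypogammaglobulinemia occurred after plasma exchange (PLEX) and was transient".

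**The concern.** Treatment policy is a normal choice for adverse events. Immunoglobulin is different because both rescue treatments act directly on the quantity being measured. After IVIg a serum Ig value includes infused immunoglobulin. After PLEX it may be low because plasma was exchanged. Neither value shows by itself what CD19 depletion has done to the subject's own Ig.

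At stake is the reading of a main pharmacodynamic safety measure of this drug. SAP 3.5.2 sets out to relate reduced Ig to infection. Protocol 7.2.2 lists infection among the causes of MG worsening, so a sequence of infection, then rescue by PLEX, then low Ig could enter the table as low Ig associated with infection. A reader of the planned tables would have no visible means of telling that sequence from infection that followed drug-related Ig loss.

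**Working it through.** **1. The protocol's own figure.** 1/81 = 1.23%, which agrees with the stated 1.2%. The exact (Clopper-Pearson) 95% interval is 0.03% to 6.7%. If post-PLEX values are set aside, and if that subject had no IgG below 200 mg/dL before PLEX (an assumption), the figure becomes 0/81, with an upper 95% limit of 4.5%. How that one case is handled decides whether the category is occupied or empty.

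**2. Does another provision separate post-rescue Ig?**

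| Provision | Effect on post-rescue Ig |
|---|---|
| SAP 3.4.1, while on-treatment option | Optional; the visible text names only TEAE, TESAE and AESI |
| Protocol 9.4, while on-treatment strategy | Also keeps data whether or not rescue was given |
| SAP 3.1.4, visit windows | Selects the observation at or before rescue for that one window; later windows can still carry post-rescue values |
| SAP 3.3.4, rescue usage | Analyses rescue use, not Ig after rescue |
| Protocol 5.2, criterion 13 | Excludes subjects with IVIg, SC Ig or PLEX in the 4 weeks before Day 1, so baseline is shielded and later values are not |

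None of these does so in the readable text. By contrast, the primary efficacy estimand in Protocol 9.4.1 does give rescue from Day 28 its own handling.

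**3. Effect on the worst-Ig category.** The worst level is a minimum over time.
- PLEX: one sample taken soon afterwards can set the minimum, and so the category, for the whole period.
- IVIg: a nadir already recorded stays, because a later rise does not change a minimum. A decline that would have appeared after IVIg can be masked.

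This table covers the combined RCP and OLP, which SAP 3.5 assigns to the any-inebilizumab set, so it is not a randomised comparison. SAP 3.5 starts that period at first IP or first inebilizumab. It is therefore unclear whether rescue given while a subject was on placebo enters the table.

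**4. Effect on the between-arm mean change (RCP).** Let p be the share of an arm with a post-rescue sample at a visit, and s the mean shift in those samples. The inebilizumab-minus-placebo difference then moves by (p for inebilizumab − p for placebo) × s. The documents give neither p nor s. The ranges below are assumptions, and all suppose more rescue on placebo.
- IVIg, 2% v 5% up to 10% v 20% (inebilizumab v placebo), s = +200 to +600 mg/dL: from (0.02 − 0.05) × 200 = −6 to (0.10 − 0.20) × 600 = −60 mg/dL. The drug looks worse.
- PLEX, 1% v 2% up to 2% v 5%, s = −200 to −600 mg/dL: from (0.01 − 0.02) × (−200) = +2 to (0.02 − 0.05) × (−600) = +18 mg/dL. The drug looks better.
- Together: from −60 + 2 = −58 to −6 + 18 = +12 mg/dL. The sign is not determined.

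**The case against.** The strongest reply is that treatment policy is right for safety. A subject with low Ig after PLEX really does have low circulating Ig. If the question is whether low Ig goes with infection, that subject is correctly classified whatever the cause. Removing such values from the main tables would delete true low readings, including the protocol's own severe case, and the resulting gaps would be informative because rescue follows deterioration. This stands. A reader might infer that treatment policy is an error here, or that the main Ig tables should exclude rescue; the documents support neither. An estimate free of rescue answers a different, additional question.

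The second reply is that text is blacked out where a rule might sit: around the quoted sentence in SAP 3.5, in the while on-treatment definition in SAP 3.4.1, and in the Ig categories and one Table 7 entry in SAP 3.5.2. This also stands, so the claim is limited to no visible rule.

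The third is that the size is unknown. A reader might scale 1/81 to this trial: 230/81 = 2.8 cases, or 115/81 = 1.4 in the randomised inebilizumab arm. Neither is a sound forecast. The rate comes from one case after two years of treatment, half of the 230 start on placebo, and the OLP is optional.

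On drug concentrations, Protocol 9.4.8 says only: "Descriptive statistics of inebilizumab concentration data will be summarized". SAP 3.6 puts PK in a separate report, so silence here does not show that post-PLEX samples will go unflagged.

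**Conclusion.** The point holds for the Ig tables. On the readable text, observed values, changes from baseline and worst-Ig categories include post-IVIg and post-PLEX values without distinction, and so mix drug effect with rescue effect.

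The documents give no rescue rate and no Ig shift, so neither the size nor the net direction can be computed. The ranges above show only that the two rescue types pull in opposite directions. A reader might infer that rescue makes inebilizumab look worse on Ig. That would need more rescue on placebo and IVIg outweighing PLEX, and the documents establish neither.

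Distortion between arms is possible in the RCP only. The tables concerned are descriptive, and no primary or key secondary test changes. The conclusion rests on IVIg adding Ig, on PLEX being able to lower it (as the NMOSD case suggests), and on no blacked-out text already supplying the separation. A SAP clarification is worth making.

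**What to change.** Keep the treatment-policy Ig tables as planned. In SAP 3.5.2, prespecify:

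1. A supplementary summary of Ig change from baseline, and a supplementary worst-Ig-by-infection table. Both omit Ig values from the start of each IVIg or PLEX course for a stated interval, or from first rescue onward. The interval needs its own justification, since the documents give no basis for its length.
2. A flag in the main worst-Ig table showing which worst values came after rescue, split by IVIg and PLEX.

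Optionally, ask that the separate PK report flag concentrations measured after PLEX.

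The cost is SAP and table-shell wording and one extra set of tables. Protocol 7.2.2 already has rescue recorded on dedicated eCRF pages, so no new data are needed. The supplementary tables will have fewer values in rescued subjects, and those values will be informatively missing. For that reason they should sit beside the main analysis and not replace it. If blacked-out text already provides this, nothing further is required.

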3.5.1 Adverse Events

In general, if an adverse event (AE) onset is on or after the first dose of IP administration during a specific study period, the AE will be considered as a treatment-emergent adverse event (TEAE) in that study period. Otherwise, the AE will be considered as a non-TEAE in that study period. The detailed definitions are included in [REDACTED]

3.5.1.1 Adverse event of special interest (AESI)

An AESI is one of scientific and medical interest specific to understanding of the IP. AESIs reported per protocol include:

- Anaphylaxis and serious hypersensitivity reactions

- Infusion-related reaction (IRR)
- Immune complex disease
- Cytopenia
- Serious and/or opportunistic infections, including Progressive multifocal leukoencephalopathy.

3.5.1.2 Analyses for Adverse Events

[figure not shown]
AEs will be coded using the most recent version of MedDRA and reported for the overall population, AChR-Ab+ population, and MuSK-ab+ population, separately. The number and percentage of subjects reporting TEAEs, TESAEs and AESIs will be summarized by SOC and PT, severity, and relationship to the IP. If a subject reports multiple occurrences of the same AE, the highest recorded severity will be taken as the severity in the summary.

An overall summary table will be produced showing the number and percentage of subjects with at least 1 TEAE in any of the following categories: TEAEs, TESAEs, Death, TEAEs leading to discontinuation of IP, Grade 3 or higher TEAEs considered related to the investigational product etc. A summary of the most common (frequency of $\geq 5\%$) TEAEs will also be presented by PT.

The TEAEs per 100 Person-years for a specific reporting period will be summarized, where $\text{TEAEs per 100 Person-years} = 100 \times \frac{\text{Total number TEAEs for a specific study period}}{\text{Total person-years for the specific study period}}$. The person-year definition is included in

A list of TEAEs, AESIs and TESAEs described in will be summarized in RCP, OLP, combined RCP and OLP and SFP as appropriate.

In addition, the overall summary of TEAEs and summary of TEAEs by SOC and PT for treatment policy will be investigated when appropriate by age, sex, region, racial/ethnic subgroups as needed for national/regional regulatory submissions, and by ADA status at any time during RCP including baseline if data allows.

3.5.2 Clinical Laboratory Evaluation

[figure not shown]
The lab data will be summarized for RCP, OLP, combined RCP and OLP, and SFP, respectively. The analyses for the laboratory results are listed in Table 7. The toxicity will be

summarized using NCI-CTCAE version 5 for the tests with objective criteria and NCI-CTCAE version 4 was used for the tests with subjective criteria. The international system of units will be used for all the lab data.

Table 7 Laboratory Results Analysis

Laboratory dataset	Planned Analysis
Hematology and Chemistry	
 • Summary of worst post-baseline toxicity grade • Summary of at least 2-grade shift from the baseline to the worst post-baseline toxicity grade • Summary of shift from the baseline relative to the normal range • Summary of observed values, change from baseline and percent changes from baseline •
Immunoglobulins	
 • Summary of observed values and changes from the baseline

To evaluate the association between reduced Ig levels and infections/serious infections /opportunistic infections, **proportions of subjects with these AEs** will be summarized by the worst Ig Level during the combined RCP and OLP by the categories listed in [REDACTED]. **Additionally, TEAEs by SOC and PT during the combined RCP and OLP will be summarized by the categories listed in [REDACTED] as well.**

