23. Any of the following laboratory abnormalities at screening (one repeat test may be conducted to confirm results prior to randomization within the same screening period):
  - a. Elevated liver enzymes (aspartate aminotransferase [AST] or alanine aminotransferase [ALT]  $> 2.5 \times$  upper limit of normal [ULN])
  - b. Total bilirubin  $> 1.5 \times$  ULN (unless due to Gilbert's syndrome)
  - c. Estimated glomerular filtration rate  $< 45$  mL/min/1.73 m^2
  - d. CD19+ B-cell count  $< 40$  cells/ $\mu$ L
  - e. Absolute neutrophil count  $< 1.2 \times 10^3$  cells/ $\mu$ L
  - f. Platelet count  $< 75,000/\mu$ L (or  $< 75 \times 10^9/L$ )
  - g. Hemoglobin  $< 8.0$  g/dL
  - h. Total Ig  $< 600$  mg/dL
24. Positive test for chronic hepatitis B infection at screening, defined as either 1) positive hepatitis B surface antigen (HBsAg) or 2) a positive hepatitis B core antibody (anti-HBc) PLUS negative hepatitis B surface antibody (anti-HBs).  
Note: Subjects with a positive anti-HBs only, or a positive anti-HBc plus positive anti-HBs and negative HBsAg, are eligible to enroll.
25. History of untreated hepatitis C infection, or positive antibody test for hepatitis C virus (HCV) unless the subject is considered to be cured following antiviral therapy and has an HCV viral load below the limit of detection  $\geq 24$  weeks after completion of treatment at site or central lab.
26. Positive HIV test.
27. Blood transfusion within 4 weeks prior to screening or during the screening period.
28. Inability to read.
29. History of active or latent tuberculosis (TB), or a positive QuantiFERON®-TB Gold test at screening, unless treatment for TB was completed per local guidelines. Subjects with latent TB or a positive QuantiFERON®-TB Gold test who are actively on anti-TB treatment can enroll if they have completed  $\geq 1$  month of anti-TB treatment and intend to complete the full course of anti-TB treatment. Subjects with an indeterminate QuantiFERON®-TB Gold test result can enroll if a repeat QuantiFERON®-TB Gold is negative or a tuberculin skin test is negative.
30. Hospitalization for any reason  $< 30$  days prior to randomization.
31. Current or recent MG deterioration that has not returned to baseline/resolved within  $\geq 30$  days prior to randomization.

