3.1 General Considerations

All efficacy analyses described below apply to the RCP unless stated otherwise. The efficacy endpoints will be summarized at scheduled visits during RCP and OLP in the overall study population, AChR+-Ab+ population, and MuSK+-Ab + population, respectively. For subjects in the OLP, the efficacy may also be summarized over the combined RCP and OLP to characterize the durability of the treatment effect, if applicable.

[figure not shown]
The safety endpoints will be summarized for the RCP, OLP and combined study periods, respectively in the overall study population, AChR+-Ab+ population, and MuSK+-Ab + population, respectively.

Tabular summaries will be presented by treatment group. Categorical data will be summarized by the number and percentage of subjects in each category. [REDACTED]

All hypothesis testing will be reported using 2-sided tests. Unless otherwise stated, nominal p-values will be reported. P-values will be rounded to 4 decimal places. The 95% confidence interval (CI) will be reported as appropriate.

The absolute change from baseline is computed as (visit value – baseline value). Percent change from baseline is computed as (visit value – baseline value) / baseline value x 100%. If either a visit value or the baseline value is missing, the absolute change from baseline and the percent change from baseline will also be set to missing.

All statistical calculations will be primarily performed using SAS® System Version 9.4 or higher.

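### The readable SAP plans no by-arm count of low immunoglobulin from laboratory data in the placebo-controlled period

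*SAP*

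**What the plan says.** SAP 3.5.2 says "The lab data will be summarized for RCP, OLP, combined RCP and OLP, and SFP, respectively", and SAP 3.1 says "Tabular summaries will be presented by treatment group". Immunoglobulins are therefore summarised against placebo in the RCP. What is summarised differs by row of Table 7:

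- **Haematology and chemistry:** worst post-baseline toxicity grade, shifts of at least two grades, "Summary of shift from the baseline relative to the normal range", and observed values with changes.
- **Immunoglobulins:** "Summary of observed values and changes from the baseline", and nothing else.

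Ig categories appear once, below the table. Proportions of subjects with infections "will be summarized by the worst Ig Level during the combined RCP and OLP by the categories listed in" a redacted reference, and TEAEs are tabulated by the same categories. SAP 3.5 fixes the set for that period: "For the combined RCP and OLP, the safety analysis will be based on the any inebilizumab analysis set using treatment-policy strategy". SAP 3.1.2 limits that set to subjects with at least one inebilizumab dose.

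The protocol describes low Ig by thresholds. Section 2.1.4 defines severe hypogammaglobulinaemia as IgG below 200 mg/dL and reports one case in 81 (1.2%) after two years in the NMOSD study; that case followed plasma exchange and was transient. Exclusion criterion 23h in section 5.2 is "Total Ig $< 600$ mg/dL". Protocol 9.4.7 plans risk differences with 95% CI for RCP safety, and laboratory shifts from baseline, each where applicable.

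**The concern.** Low Ig matters in the lower tail, and it is a plausible consequence of depleting B cells. Observed values and changes describe the centre and perhaps the spread of the distribution. They do not say how many subjects crossed a threshold.

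The RCP is the only part of the trial where that number can be set against a concurrent control. Subjects enter on corticosteroids, other immunosuppressants or both, steroids are tapered, and rescue is IVIg or PLEX. All of these could affect Ig or its interpretation. In the combined RCP and OLP every subject has had inebilizumab, so a count there cannot be attributed by comparison. At stake is whether the trial can state an excess risk of low Ig over placebo from data it already plans to summarise.

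**Working it through.** **1. Where a by-arm low-Ig count could come from**

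| Source | Period | Randomised comparator? | Counts subjects below an Ig threshold? |
|---|---|---|---|
| Table 7, Immunoglobulins row | RCP and others | Yes, in the RCP | No; values and changes only |
| Worst-Ig categories, SAP 3.5.2 | Combined RCP and OLP | No; any-inebilizumab set | Used to group adverse events |
| TEAEs by SOC and PT, SAP 3.5.1.2 | Includes the RCP | Yes | Only cases reported as AEs |
| Laboratory shifts, protocol 9.4.7 | Not fixed for Ig | Possible | Conditional; not carried into the Ig row |

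No row combines a randomised comparator with a planned laboratory count. SAP 3.5 starts the combined period at first IP or first inebilizumab dose, so placebo subjects who cross over may contribute RCP time. Placebo subjects who never cross over are still left out, so this is not a comparison of randomised groups.

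**2. The adverse-event route.** Hypogammaglobulinaemia is not among the AESIs readable in SAP 3.5.1.1. Protocol 7.3.3 withholds B-cell counts and a redacted item from sites up to OLP Day 15. Whether the redacted item is Ig cannot be read. If it is, investigators would rarely see a low value to report.

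**3. The same mean change can hide different counts.** The documents give no Ig distribution, so these inputs are assumed: baseline total Ig is normal with mean 1100 and SD 280 mg/dL, truncated at the entry limit of 600. The truncated mean is 1123.6 and the SD 257.0. There are 230/2 = 115 subjects per arm.

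- Pattern A: everyone falls 10%.
- Pattern B: 10% of subjects fall 55% and 90% fall 5%. The average fall is 0.1 × 55% + 0.9 × 5% = 10%.
- Mean change in both: -0.10 × 1123.6 = -112 mg/dL.

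Share below 600, with P(X < x) = [Φ((x - 1100)/280) - 0.0371] / 0.9629:

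- A: P(X < 600/0.90 = 666.7) = (0.0609 - 0.0371)/0.9629 = 2.5%, and 115 × 0.0247 = 2.8 subjects.
- B: 0.9 × P(X < 600/0.95 = 631.6) + 0.1 × P(X < 600/0.45 = 1333.3) = 0.9 × 0.0105 + 0.1 × 0.7899 = 8.8%, and 115 × 0.0884 = 10.2 subjects.

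Range: with baseline mean 1000 to 1300 and SD 200 to 350, the same formulas give 0.1% to 5.0% for A and 5.7% to 10.4% for B.

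SD of change: A, 0.10 × 257.0 = 26. B, √[0.0325 × (257.0² + 1123.6²) - 112.4²] = 175, where 0.0325 = 0.9 × 0.05² + 0.1 × 0.55².

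Neither pattern reaches 200 mg/dL; the lowest possible value is 600 × 0.45 = 270.

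**4. What the added table could show.** Assumed counts of 12 and 2 of 115 give 10.4% - 1.7% = 8.7 points (Newcombe 95% CI 2.5 to 15.7). In the MuSK-Ab+ group, 2 and 0 of 21 give 9.5 points (-7.4 to 28.9), which is nearly uninformative. For severe cases, if the NMOSD rate applied, 115/81 = 1.4 would be expected and the chance of at least one would be 1 - (80/81)^115 = 76%. That rate is after two years, so the RCP count may well be lower.

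**The case against.** A reader might infer that low-Ig incidence will never be reported against placebo. The documents do not support that. TEAEs are tabulated by preferred term and by treatment group in the RCP, so a low-Ig event reported as an AE would be counted. Protocol 9.4.7 also leaves room for laboratory shifts and does not exclude Ig. What is missing is a planned count from the laboratory values themselves.

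A reader might also infer that only means will be shown. The SAP does not say so. It refers to observed values, and the general text in 3.1 on summaries is partly redacted, so SDs, medians and minima may be included. In the illustration an SD of 26 against 175 would plainly separate the two patterns. It would still give neither a number of subjects nor a risk difference.

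Redaction is a fair caution. The category definitions are hidden, numbering jumps from Table 7 to Table 9, and part of 3.5 is blacked out. The revision history mentions a sponsor AESI definition and an AE summary by FMQ that are not readable. The point therefore applies to the readable text, but the Immunoglobulins row and the sentence tying the categories to the combined period are both legible.

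Finally, the RCP comparison is not free of rescue. RCP safety data are kept regardless of rescue use, and IVIg or PLEX can alter Ig. That calls for marking such values; it does not remove the need for the count.

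**Conclusion.** The point holds as a moderate gap in planned safety reporting. In the readable text, no low-Ig incidence by arm is pre-specified from RCP laboratory data, and the SAP's own Ig categories are applied only where there is no randomised comparator. The illustration puts the difference that an average can hide at about 3 against 10 subjects of 115. It rests on an assumed baseline distribution and assumed patterns of decline, uses the total-Ig entry limit as the cut-off, and shows no missed severe case. The conclusion also assumes that the redacted text holds no such table and that Ig is sampled in both arms during the RCP, as the planned RCP summaries imply. Efficacy conclusions and type I error are unaffected.

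**What to change.** Extend the Immunoglobulins row of SAP Table 7 for the RCP, using the Safety Analysis Set by treatment actually received (as SAP 3.1.2 defines it), overall and by antibody population:

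1. Number and percentage of subjects by worst post-baseline Ig category, using the categories already referred to in 3.5.2.
2. Shift from baseline category to worst post-baseline category.
3. Risk difference against placebo with 95% CI, as protocol 9.4.7 allows.
4. A flag or footnote for values taken after IVIg or PLEX rescue.

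State the time span in the table, because the RCP lasts 26 weeks in the MuSK-Ab+ population and 52 weeks in the AChR-Ab+ population.

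The cost is one or two descriptive tables from data and categories the trial already has. Counts will be small and intervals wide in the MuSK-Ab+ group (21 per arm). No visit, sample, clinical rule, efficacy analysis or alpha allocation changes.
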